13.1.2 Adverse Device Effect

An adverse device effect (ADE) is an AE related to the use of an investigational medical device. This definition includes AEs resulting from insufficient or inadequate instructions Clinical Study Protocol

for use; deployment, implantation, installation, or operation; or any malfunction of the investigational medical device. This definition also includes any event resulting from use error or from intentional misuse of the investigational medical device.

13.1.3 Anticipated Serious Adverse Device Effect

An anticipated serious adverse device effect (ASADE) is a serious adverse device effect which by its nature, incidence, severity or outcome has been previously identified in the investigational plan or application (including a supplementary plan or application) and/or in the risk analysis report. ASADEs may include but are not limited to:

- Corneal ulcer (infectious or non-infectious)
- Keratitis
- Sensitivity to light (photophobia)
- Excessive eye secretions including mucopurulent discharge
- Blurred vision, rainbows or halos around objects
- Poor visual acuity (reduced sharpness of vision)
- Moderate to severe eye pain not relieved by removing the lens

13.1.4 Unanticipated Adverse Device Effect

An unanticipated adverse device effect (UADE) is any serious adverse effect on health or safety or any life-threatening problem or death caused by, or associated with a device, if that effect, problem or death was not previously identified in nature, severity or degree of incidence in the investigational plan or application (including a supplementary plan or application), or any other unanticipated serious problem associated with a device that relates to the rights, safety, or welfare of subjects.

13.1.5 Serious Adverse Events (SAE)

- Serious adverse event is an AE that:
 - o Led to death;
 - o Led to serious deterioration in the health of the subject, that resulted in:
 - A life-threatening illness or injury; or
 - A permanent impairment of a body structure or a body function (eg, blindness); or
 - Inpatient or prolonged hospitalization; or
 - Medical or surgical intervention to prevent life-threatening illness or injury or permanent impairment to a body structure or a body function;
 - Led to fetal distress, fetal death, or a congenital abnormality or birth defect.

NOTE: Planned hospitalization for a pre-existing condition, or a procedure required by the protocol, without serious deterioration in health, is not considered an SAE.

Serious adverse events are those events that result in, or have potential to cause, either permanent impairment of an ocular function or damage to an ocular structure and may necessitate medical or surgical intervention.

Serious adverse events may include any hazardous, **sight-threatening conditions** occurring after exposure to the test article, including the following:

- A presumed infectious ulcer (defined as a progressive erosion of the corneal tissue). For the purposes of reporting, this includes:
 - o Central or para-central location;
 - o Penetration of Bowman's membrane;
 - o Infiltrate ≥ 2 mm diameter;
 - o Associated with iritis Grade ≥ 2 ;
 - Associated with any increase in intraocular pressure;
 - o Culture positive for microorganisms;
 - o Increasing size or severity at subsequent visits;

Note: Signs of a presumed infectious corneal ulcer may include irregular focal infiltrates, active lesions with raised edges, significant diffuse infiltration, anterior corneal to mid-stromal involvement, erosion with overlying staining, conjunctival and lid edema, anterior chamber reaction (iritis), and severe bulbar and limbal redness. Symptoms associated with a presumed infectious ulcer (microbial keratitis) may include pain of rapid onset, severe redness, purulent or mucopurulent discharge, tearing, and photophobia.

- Any central or paracentral (within 6 mm of cornea) corneal event that results in permanent opacification (such as vascularization);
- Any serious adverse ophthalmic events including hypopyon and hyphema;
- Any neovascularization within the central 6 mm of the cornea;
- Permanent loss of ≥2 lines of BSCVA;
- All cases of iritis.

13.1.6 Significant Non-Serious Adverse Events

Significant non-serious AEs should include:

- Peripheral non-progressive non-infectious corneal ulcers;
- All symptomatic corneal infiltrative events;
- All cases of corneal staining Grade ≥ 3 ;
- A temporary loss of ≥2 lines of BSCVA (for ≥2 weeks);
- Neovascularization cases Grade ≥2.

Any ocular event that necessitates temporary lens discontinuation of ≥ 2 weeks

13.1.7 Non-Significant Non-Serious Adverse Events

Non-significant non-serious AEs may include but are not limited to:

- Bacterial conjunctivitis;
- Viral conjunctivitis;

- Allergic conjunctivitis;
- Corneal edema;
- Contact lens-related papillary conjunctivitis; and,
- Loss of contrast sensitivity.

13.2 Adverse Event Treatment and Culturing

With any AE, treat the subject as appropriate to prevent further complications and to potentially resolve the event consistent with the standard of care.

For purposes of this study, the Sponsor requests that cultures should be obtained in cases of corneal ulcer or suspected ocular infection, unless medically contraindicated. Cultures should be taken from the cul-de-sac, lower eyelid margin, and the corneal lesion (if applicable). The culturing techniques are outlined in APPENDIX F.

When a culture is obtained, the contact lenses and contact lens cases which were being utilized by the subject at the time of the AE should be collected from the subject for culturing and processing by the clinical lab designated by the site.

Microbial data generated from returned subject supplies (eg, lenses, lens cases, and/or lens case solutions) are for information only. Because microbes may be introduced into subject supplies during use, recovery of microbes from returned subject supplies cannot be presumed to indicate etiology or direction of organism transmission.

The ocular cultures, along with the associated contact lenses and contact lens cases, will be sent to the clinical laboratory designated by the site for analysis. The clinical laboratory will report the culture results to both the Investigator and to the Sponsor.

13.2.1 Medical Treatment Including Non-Adverse Events

In the event that a subject requires medical treatment (prescription medication) for an ocular condition, treat the subject as appropriate to prevent further complications and to potentially resolve the event.

13.3 Evaluations

When evaluating AEs, the Investigator must determine if the event is serious (refer to Section 13.1.5 for criteria) and assess the severity of symptoms and the relationship of the event to the study device using the following guidelines:

13.3.1 Severity

- **Mild:** Subject awareness of a sign or symptom that is easily tolerated, requires no treatment, and does not interfere with subject's daily activities.
- Moderate: Subject awareness of a sign or symptom which may be a low level of
 concern to the subject and may interfere with daily activities but can be relieved
 by simple therapeutic care.
- **Severe:** A sign or symptom that interrupts the subject's daily activity and requires systemic therapy or other treatment.

13.3.2 Relationship to Study Device and/or Rewetting Drops

- **Related:** There is at least a reasonable possibility that the AE/SAE is related to the study device and/or Rewetting Drops. Reasonable possibility means that there is evidence to suggest a causal relationship or association between the study device and/or Rewetting Drops and the AE. Also referred to as an ADE.
- Unrelated: There is little or no reasonable possibility that the AE/SAE is related to the study device and/or Rewetting Drops. This assessment implies that the AE/SAE has no evidence to suggest either a causal relationship or association to the study device and/or Rewetting Drops and a more likely or certain alternative etiology exists.

13.4 Procedures for Reporting Serious Adverse Events, Unanticipated Adverse Device Events, and Significant Non-Serious Adverse Events

Events classified as SAE/UADE or significant non-serious AEs require expeditious handling and reporting to the Sponsor or designee to comply with regulatory requirements, as follows:

•	Must be immediately reported to the Medical Monitor within 24 hours of
	knowledge of the event using the Sponsor-provided form (SAE/UDE reporting
	form) by emailing the completed form to
	Medical Monitor will email a copy of the form to:
	·
	upon receipt. The Medical Monitor will email/fax
	a copy of the form immediately (within 24 hours) for SAEs only to
	upon receipt.

- Investigators should not wait to receive additional information to fully document the event before notifying the medical monitor and Sponsor/designee of an SAE/UADE/significant non-serious AE. If only limited information is initially available, follow-up reports are required. Additional relevant information such as hospital records and autopsy reports should be provided to the Sponsor/designee as soon as they are available.
- The Investigator should take all appropriate measures to ensure the safety of the subjects: notably, he/she should follow a subject with an SAE/UADE/significant non-serious AEs until the event has resolved or the condition has stabilized. This may imply that follow-up will continue after the subject has left the study, and that additional evaluations may be requested by the Sponsor.

In the case of an AE (serious and significant non-serious) or medical treatment (non-AE), the Investigator must:

- Report the AE or medical treatment to the Medical Monitor and Sponsor/designee within 24 hours of knowledge of the event using the Sponsor-provided form (SAE/UADE Report Form) by emailing the completed form to the Medical Monitor and Sponsor/designee.
- Indicate on the Initial SAE/UADE Report Form whether the SAE/UADE is presumed to be not study related, lens related, solution related, or both lens/solution related.

- Ensure that the subject's identity is protected and the subject's identifiers in the clinical trial are properly mentioned on the form.
- BEGIN TREATMENT OF THE AE IMMEDIATELY BY A SUITABLY LICENSED EYE CARE PROFESSIONAL.
- Enter the SAE/UADE/significant non-serious AE into the eCRF within 3 business days of submitting the Initial SAE/UADE Report Form.
- Continue to update the eCRF, if applicable, each time the subject is seen during the management of the incident and at resolution of the incident. Whenever possible, it is suggested that the Investigator take photographs of all AEs and forward them to the Sponsor.
- Cases requiring medical treatment will be evaluated by the Sponsor. Upon review of the medical treatment, Bausch + Lomb Clinical Operations representatives may contact the Investigator to request further information concerning the treatment.
- Submit all bills, prescription receipts, and culture reports/fees related to the AE to Bausch + Lomb Clinical Operations. Expenses incurred for study-related medical treatment will be paid by Bausch + Lomb Clinical Operations.

Actions required by Investigators for reporting non-serious ocular AEs in the study eye(s) are summarized below.

Table 2. Non-serious Adverse Events

Non-device-related	Device-related	
Recorded on AE CRF only;		
No expedited report to Sponsor;		
No report to IRB		
	Recorded on AE CRF only; No expedited report to Sponso	

Actions required by Investigators for reporting all SAEs in the study eye(s) and/or non-study eye are summarized below.

Table 3. Serious Adverse Events, Unanticipated Device Adverse Events and Significant Non-Serious Adverse Events

SAEs (ocular and non-		Device-relate	d
ocular), UADE, significant	Non-device-		
non-serious AE	related	Anticipated	Unanticipated
Required action	Recorded on SAE/U	JADE Report	Recorded on SAE/UADE Report
	Form and AE CRF		Form and AE CRF
	Û		Û
	Investigator submits expedited		Investigator submits expedited report
	report to Sponsor and its		to Sponsor and its representative
	representative within 24 hours;		within 24 hours; Investigator reports
	Report to IRB, if re	quired per	to IRB within 10 working days or
	IRB policy		per IRB policy, whichever is shorter
			Sponsor conducts evaluation
			Û
			Sponsor or its representative reports
			to FDA, all IRBs, and all
			Investigators within 10 working days

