10.4 Other Materials

10.4.1 Care System

All subjects will be dispensed the following care products for use during the study:

- Biotrue Multi-Purpose solution for daily rinsing, cleaning, disinfecting, and storing their lenses in lens cases. All commercially available Biotrue bottles include a green lens case.
- ReNu MultiPlus Lubricating and Rewetting Drops for use as needed during the study

Investigators will be provided Biotrue Multi-Purpose solution and lens cases for return of study lenses to the Sponsor at the end of the study.

NOTE: Use of other contact lens care products is not allowed during the study.

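### Sections 13.1.2, 13.3.2 and the SAE/UADE report form attribute adverse events by three inconsistent schemes, and 13.3.2 has no place for the Biotrue solution

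*Combined protocol and SAP*

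**What the plan says.** Four parts of the protocol bear on how an adverse event is attributed.

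- **Definition (13.1.2).** "An adverse device effect (ADE) is an AE related to the use of an investigational medical device". Neither the drops nor the care solution is mentioned. The comparator is not named either, although the general AE definition in 13.1.1 does name it.
- **Scale (13.3 and 13.3.2).** Section 13.3 asks the investigator to judge "the relationship of the event to the study device using the following guidelines". The guideline that follows widens the object of that judgement. An event is Related if "There is at least a reasonable possibility that the AE/SAE is related to the study device and/or Rewetting Drops", and such an event is "Also referred to as an ADE". The only other category is Unrelated: "There is little or no reasonable possibility that the AE/SAE is related to the study device and/or Rewetting Drops". That category also implies a more likely or certain alternative cause.
- **Form (13.4).** On the Initial SAE/UADE Report Form the investigator marks the event as "presumed to be not study related, lens related, solution related, or both lens/solution related".
- **Exposure (10.4.1).** Every subject is given two care products. The first is "Biotrue Multi-Purpose solution for daily rinsing, cleaning, disinfecting, and storing their lenses in lens cases". The second is the ReNu MultiPlus rewetting drops, taken when needed. Both arms receive both products.

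Section 13.1.1 requires AEs to be split into device related and non-device related. Tables 2 and 3 are laid out by that split.

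**The concern.** The study objective is the safety and efficacy of a lens. Safety reporting needs one rule for deciding when an event is attributed to the lens rather than to a product used with it. Here the ADE label has two meanings, one of the two care products has no category on the general scale, and the expedited form divides events in a way that cannot be mapped back to the scale.

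Two things are at stake. The first is the device-related classification of adverse events, and any ADE summary later built on it. The second is routing under Table 3. There, an unanticipated device-related event goes to the IRB within 10 working days or per IRB policy, whichever is shorter. It is then evaluated by the sponsor and reported to FDA, all IRBs and all investigators. A non-device-related event does not follow that route.

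**Working it through.** No figure in the plan is at issue, so the check sets the passages side by side. Take an event that the investigator attributes to one source and apply each rule as written.

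| Judged cause | ADE under 13.1.2 | 13.3.2 | Form in 13.4 |
|---|---|---|---|
| Test lens only | Yes | Related, ADE | Lens related |
| Control lens only | Not stated; comparator not named | Related, ADE, if study device covers both lenses | Lens related |
| Rewetting drops only | No | Related, ADE | Unclear; solution is not defined |
| Biotrue only | No | Unrelated | Solution related |
| Test lens and Biotrue | Yes | Related, ADE | Both |

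1. *Drops only.* 13.1.2 and 13.3.2 give opposite answers on ADE status. The form has no clear box.
2. *Biotrue only.* There is little link to lens or drops, and Biotrue itself is the more likely alternative cause, so the wording of Unrelated is met. The form would mark the same event solution related.
3. *Which events the form covers.* Section 13.4 sends SAEs, UADEs and significant non-serious AEs to the SAE/UADE form, although the attribution instruction names only SAE/UADE. Lens versus solution is therefore largely recoverable for these events, apart from the place of the drops. Table 2 puts the other non-serious ocular AEs on the AE CRF only, and for these the protocol text gives no scheme beyond 13.3.2.
4. *Routing.* As far as the tables can be read, Table 2 requires the same action in both columns. In Table 3, non-device-related and anticipated device-related events share one action. Only the unanticipated device-related column differs. A serious unanticipated Biotrue reaction, scored Unrelated under 13.3.2, could fall outside it.

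**Illustration on assumed rates (none is in the documents).** Let the lens-related ADE risk be p = 4% (test) and 2% (control). Let the drop-reaction risk q be the same in both arms and independent of p. The recorded ADE risk is 1 − (1 − p)(1 − q).

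- q = 0: 0.040 and 0.020; difference 0.020, ratio 2.00.
- q = 1%: 1 − 0.96 × 0.99 = 0.0496 and 1 − 0.98 × 0.99 = 0.0298; difference 0.0198, ratio 1.66.
- q = 5%: 1 − 0.96 × 0.95 = 0.088 and 1 − 0.98 × 0.95 = 0.069; difference 0.019, ratio 1.28.

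At q = 5%, the share of subjects counted with an ADE who have no lens-related event is 1 − 0.04/0.088 = 55% (test) and 1 − 0.02/0.069 = 71% (control). At q = 0 the effect is nil.

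Equal q is itself an assumption, because drops are used as needed after randomization and the two lenses are of different materials. With about 56 and 28 subjects per arm (section 9.5), one reclassified subject moves the subject-level rate by 1/56 = 1.8 percentage points in the test arm or 1/28 = 3.6 in the control arm.

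**The case against.** The strongest reply is that this is a mismatch of terms with little analytic consequence. Much of that reply stands.

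- The primary safety endpoint (14.1.2) is the proportion of eyes with a slit lamp finding above Grade 2 and uses no causality judgement. The supplied text specifies no ADE-count analysis, and section 14.7 defers full analyses to a separate SAP. This stands.
- Unrelated to lens or drops, and solution related, can both be true of one event, and Table 3 requires both records. This stands for SAEs and UADEs, but it does not settle which column of Table 3 applies.
- Infiltrates, ulcers and neovascularization are presumed device related unless there is another explanation (13.1.1). This limits drift into Unrelated. It does not cover an event for which Biotrue is that other explanation.
- The AE eCRF is not supplied and may contain further attribution fields. This stands, so the point rests on the protocol's rules and not on the form's content.
- Using Biotrue could be seen as part of using the lens, which would bring its reactions under 13.1.2. That reading sharpens the conflict, because 13.3.2 would still allow Unrelated.

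A reader might infer that lens-related event counts are misclassified, or that the test–control comparison is biased. The documents do not support either. They show how misclassification could arise, not that it does. Both arms receive the same care products, and equal reaction rates would leave the risk difference almost unchanged.

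A reader might also infer that control-lens reactions are excluded from ADEs. The text leaves this unstated but does not say so: 13.3 refers to the study device, and 13.1.1 includes the comparator.

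**Conclusion.** The contradiction is real and can be checked from the text alone. Drop-only reactions are ADEs under 13.3.2 but not under 13.1.2. Biotrue-only reactions have no category in 13.3.2 except Unrelated. The form's scheme does not map onto either section. Device-related classification can therefore be wrong or inconsistent, mainly for AEs outside the expedited form, and one reporting route in Table 3 is exposed.

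The size is limited. No primary endpoint, success criterion, power figure or sample size changes. The number of events affected cannot be derived, and it is zero if no drop or solution reactions occur. The conclusion assumes that sites apply the text as written and that the AE CRF follows 13.3.2. Whether the drops or Biotrue count as medical devices cannot be settled from the documents, which call only the test lens investigational.

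**What to change.** Reconcile 13.1.2, 13.3.2 and the form instruction in 13.4.

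- Use one attribution on both the AE CRF and the SAE/UADE form: relationship to the study lens, to the rewetting drops and to the care solution, each related or unrelated, with more than one allowed.
- Limit the ADE label in 13.1.2 and 13.3.2 to events related to the study lens, and state that this covers both test and control lenses.
- State which column of Table 3 applies to an event related only to the drops or the care solution.

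The cost is protocol wording, matching fields on the two forms, and slightly more investigator entry per AE. It is best done before data collection, because later reconstruction would mean querying sites again. Wording alone could remove the clash over the ADE label. The separate relationship fields are what allow lens attribution to be recovered for events not on the expedited form.

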13.4.1 On-Site Serious Adverse Event and Unanticipated Adverse Device Effect Reporting

The site must report any SAE or UADE on a SAE/UADE report form and any available documents 24 hours of becoming aware of an event.

The contacts for reporting SAEs/UADEs are:

The site must also report UADEs to the reviewing IRB within 10 working days following awareness of the UADE or according to the established reporting procedures of the IRB, whichever is shorter. The site should also complete applicable CRFs within 3 working days of event identification. The Sponsor or its representative will report the UADE to the FDA, all other IRBs, and all Investigators within 10 working days after first being informed by the Investigator.

13.4.2 Off-Site Unanticipated Adverse Device Effect Reporting

When participating in multicenter clinical investigations, Principal Investigators may receive off-site UADE reports. These are Sponsor reports of UADEs which occurred at other clinical sites for the same trial, or in different trials using the same test article, that met the criteria for reporting to a regulatory agency. These should be reported to the reviewing IRB within 10 working days or per their established reporting procedures, whichever is shorter.

Clinical Study Protocol

13.4.3 Reporting Device Deficiencies

A device deficiency is defined as an inadequacy of a medical device with respect to its identity, quality, durability, reliability, safety, or performance. Device deficiencies include malfunctions, use errors, and inadequate labeling.

Investigators must evaluate, record, and report via applicable forms any complaints/ deficiencies or malfunctions experienced with a test or control lens during this trial to the Sponsor and its representative promptly. The Sponsor shall review all device deficiencies and, upon the Sponsor's request, Investigators must supply any additional information related to the safety reporting of a particular event.

The contact for reporting device deficiencies is:

The Sponsor shall review all device deficiencies and determine and document in writing whether they could have led to an SAE. In the event of a disagreement between the Sponsor and the Investigator(s), the Sponsor shall communicate both opinions to the reviewing IRB per their established reporting procedures and the health authority.

